A DLT will be defined as the occurrence of any toxicities in Table 2 occurring up to and during Day 28 of Cycle 1, except those with a clear alternative explanation (e.g., disease progression) or transient (≤ 72 hours) abnormal laboratory values without associated clinically significant signs or symptoms based on investigator and sponsor determination. All DLTs will be assessed by the investigator using CTCAE v5 criteria (NCI 2018). In order to be included in the tolerability review, subjects must have received the cohort-specific dose of itacitinib and everolimus for at least 75% of the days during the 28-day surveillance period of Cycle 1 or have experienced a

Itacitinib + everolimus in HL
Version 11.0
Page 16 of 72

	DLT. Additional subjects may be enrolled to achieve a minimum cohort size should withdrawal or dose interruptions/reductions result in subjects being non-evaluable. The maximum tolerated DLT rate is set to be 30%. During Phase II portion of the study, a Bayesian stopping rule will be employed to monitor excess DLT rate. Under the assumption of a beta prior of (1,5), that is 1 DLT in 6 patients, the study will be stopped if 4 in 6, 5 in 9, 6 in 12, or 7 in 15 DLT are observed during cycle 1 in phase II of the study. The posterior probability that the true DLT rate is above 30% at each stopping would be around 77 to 79%.
	Subjects who experience a DLT or an unacceptable toxicity (i.e. not able to resume therapy within 28 days due to unresolved toxicity) beyond the DLT window will be also considered in the determination of the RP2D dose.
	Any grade 5 hematologic and non-hematologic event related to the study treatments (at any time) will be considered a DLT.
Data and Safety Monitoring Plan	This study will be monitored according to the Sponsor Data and Safety Monitoring Plan.

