3.1.3 Study Intervention Phase II

Subjects with cHL will receive the recommended Phase II dose (RP2D) of itacitinib in combination with everolimus as determined in Phase 1. Phase II will enroll 8 to 17 subjects depending on Cohort expansion in the Phase I portion. Since 6 of the Phase I subjects will be recruited, treated and followed in the same way as the Phase II subjects, they will be considered as accrued to the Phase II study as well. At least 14 subjects will be treated at RP2D level and evaluable for CR rate. Using a Simon 2-stage optimal design, if there are no responders with CR by the 16 week response assessment from the first 9 evaluable subjects at the RP2D, the null hypothesis will be considered as supported, and the study will be terminated. If there are no CRs in the first several patients (week 8 or 16 assessment), we will suspend the study enrollment and await final response assessment on all 9 patients (until week 16). The study will be considered successful if the total number of subjects with CR is \geq 2 in Phase II.

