3.2 DLT Definition

A DLT will be defined as the occurrence of any toxicities in Table 2 occurring up to and including Day 28 of Cycle 1, except those with a clear alternative explanation (e.g., disease progression) or transient (≤ 72 hours) abnormal laboratory values without associated clinically significant signs or symptoms based on investigator and sponsor determination. All DLTs will be assessed by the investigator using CTCAE v5 criteria (NCI 2018). In order to be included in the tolerability review, subjects must have received the cohort-specific dose of itacitinib and everolimus for at least 75% of the days during the 28-day surveillance period of Cycle 1 or have experienced a DLT.

Individual subject dose reductions may be made based on events observed at any time during treatment with study drug (see Section 5.6); however, for the purposes of dose cohort escalation/de-escalation, expanding a dose cohort, and determining the RP2D, decisions will be made based on events that are observed from the first day of study drug administration through and including Day 28. A lower RP2D may subsequently be determined based on relevant toxicities that become evident after Day 28.

Subjects who experience a DLT or an unacceptable toxicity (i.e. not able to resume therapy within 28 days due to unresolved toxicity) beyond the DLT window will be also considered in the determination of the RP2D dose.

Any grade 5 hematologic and non-hematologic event related to the study treatments (at any time) will be considered a DLT.

Table 2: DLT defining toxicities

TOXICITY

Non-hematologic

- Any \geq Grade 3 non-hematologic toxicity, EXCEPT the following:
 - Transient (≤ 72 hours) abnormal laboratory values without associated clinically significant signs or symptoms.
 - Nausea, vomiting, and diarrhea adequately controlled with medical therapy within 48 hours.

Itacitinib + everolimus in HL
Version 11.0
Page 28 of 72

 Singular or non-fasting elevations in blood glucose (i.e., blood glucose excursions will be considered toxicities if fasting blood glucose is elevated on 2 separate sequential occasions).

Hematologic

- Grade 3 thrombocytopenia with bleeding.
- Grade 4 thrombocytopenia.
- Febrile neutropenia (ANC $< 1.0 \times 10^9$ /L and fever $> 101^\circ F/38.5^\circ C$).
- Grade 4 neutropenia that does not recover to \leq Grade 2 in \leq 3 days after interrupting study drug.
- Grade 4 anemia unresponsive to treatment for 3 days

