7 STATISTICAL PLAN

7.1 Sample size

Sample size determination: Utilizing 3 + 3 design, 6 to 15 subjects will be enrolled to Phase I portion of the trial (with at least 6 subjects treated at RP2D). Phase II will enroll 8 to 17 subjects depending on expansion needs in the Phase I portion. At least 14 subjects will be treated at RP2D level and evaluable for CR rate. The sample size for phase II was based on a decision between 2 pre-specified hypotheses about the probability of CR rate (p). The null hypothesis H₀: p = 5% reflects a response rate that would be of no clinical benefit compared to everolimus alone, and the alternative hypothesis H_a: p = 25% is a CR rate that might lead to larger, confirmatory studies. Using a Simon 2-stage optimal design, a total of 17 subjects at RP2D will be needed for 80% power at 1-sided alpha = 0.05 level. If by the 16 week visit there are no responders with CR from the first 9 evaluable subjects (at any itacitinib dose level), the null hypothesis will be considered as supported, and the study will be terminated.

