7.2.2 Interim Safety Analyses

The safety analysis is based on Bayesian probability calculations and will be performed after the first 6 subjects treated at the RP2D and then after enrollment of 9, 12, and 15 subjects at RP2D dose. The max tolerated DLT (see section 3.2) rate is 30% and a beta prior of (1,5) is assumed (that is 1 DLT in 6 subjects). The study will be terminated if 4 DLTs in 6 subjects, 5 in 9, 6 in 12, or 7 in 15 are observed. The posterior probability that the true DLT rate is above 30% at each stopping would be around 77 to 79% (79%, 78%, 78%, and 77% respectively).

If there are two (2) study related deaths in the phase I portion, the study will be terminated.

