8.7 Stopping Rules (safety and efficacy)

The safety analysis is based on Bayesian probability calculations and will be performed after the first 6 subjects treated at the RP2D and then after enrollment of 9, 12, and 15 subjects at RP2D dose. The maximum rate of unacceptable toxicity (AEs that would fit the definition of DLT from phase 1 at any point or AEs that do not allow the subject to restart treatment within 28 days) is 30% and a beta prior of (1,5) is assumed (that is 1 unacceptable toxicity in 6 subjects). The study will be terminated if 4 unacceptable toxicities in 6 subjects, 5 in 9, 6 in 12, or 7 in 15 are observed. The posterior probability that the true rate of unacceptable toxicities is above 30% at each stopping would be around 77 to 79% (79%, 78%, 78%, and 77%, respectively).

The efficacy analysis is based on Simon 2 stage optimal design and will be performed after the enrollment of the first 9 evaluable subjects treated at the RP2D. If there are no responders with CR from the first 9 evaluable subjects (at the 8 week or 16 week response assessment, at any itacitinib dose level), the null hypothesis (CR rate of 5% or lower with the new combination) will be considered as supported, and the study will be terminated. The study will be considered successful if the total number of subjects with CR is ≥ 2 in Phase II (at the 8 week or 16 week response assessment).

If there are two (2) study related deaths during the phase I portion of the trial, the study will be terminated.

Any death in the Phase II portion will result in pausing enrollment of the study until investigation is completed. If there are two (2) study related deaths in the Phase II portion of the study will be terminated.

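### One Bayesian safety stopping rule, two event windows: section 8.7 counts toxicity at any time, while 7.2.2 and the synopsis essentially count Cycle 1 DLTs, and the synopsis also names a different population

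*Combined protocol and SAP*

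**What the plan says.** The same prior, ceiling and limits appear in three places.

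- **Section 7.2.2**: "The max tolerated DLT (see section 3.2) rate is 30% and a beta prior of (1,5) is assumed". Looks fall after the first 6 subjects at the RP2D and after enrollment of 9, 12 and 15 there. Section 3.2 defines a DLT as a Table 2 toxicity up to Day 28 of Cycle 1 and adds related grade 5 events at any time.
- **Section 8.7**: same looks, limits and posterior values, but the event, which it calls unacceptable toxicity, is broader: "AEs that would fit the definition of DLT from phase 1 at any point or AEs that do not allow the subject". The second kind is failure to restart within 28 days.
- **Synopsis, Safety Evaluations**: same prior and limits, ending "6 in 12, or 7 in 15 DLT are observed during cycle 1 in phase II of the study". The synopsis also carries the any-time grade 5 sentence.

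Other text deals with late toxicity. Under 3.2, a DLT or unacceptable toxicity "beyond the DLT window will be also considered in the determination of the RP2D dose", and "A lower RP2D may subsequently be determined based on relevant toxicities that become evident after Day 28". Section 5.6 takes a subject off study if toxicity has not resolved in 4 weeks. On deaths, 7.2.2 says "If there are two (2) study related deaths in the phase I portion, the study will be terminated"; 8.7 has the same limit for Phase II and pauses enrollment after any Phase II death.

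On who is counted, 3.1.3 says of six Phase I subjects that "they will be considered as accrued to the Phase II study as well", and 7.1 sizes Phase I "with at least 6 subjects treated at RP2D". Section 4.5 instead expects 3 to 6 Phase I subjects to be carried over.

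**The concern.** The shared prior, limits and posterior values show that this is meant to be one rule. It is a mandatory one: reaching a limit ends the study. Yet the number entered depends on which section is open. Treatment is daily for up to 24 cycles, and a Cycle 1 count covers only the first. For non-fatal toxicity after Day 28, section 8.7 holds the only numeric study-level limit, and the other two statements of the rule leave those events out. A monitoring committee working from 7.2.2 could see no trigger where 8.7 requires termination. The synopsis adds a second mismatch, because Phase II subjects are not the same set as subjects treated at the RP2D.

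**Working it through.** **1. Reproduce the stated posteriors.** With x events in n subjects and a Beta(1,5) prior, the posterior is Beta(1+x, 5+n−x), and the rule uses P(rate > 0.30).

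| x/n | Posterior | P(rate > 0.30) | Plan |
|---|---|---|---|
| 4/6 | Beta(5,7) | 0.790 | 79% |
| 5/9 | Beta(6,9) | 0.780 | 78% |
| 6/12 | Beta(7,11) | 0.775 | 78% |
| 7/15 | Beta(8,13) | 0.772 | 77% |

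The arithmetic of the rule is right. Only the count fed into it is in doubt.

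**2. Apply both counts to the same subjects.** Six subjects at the RP2D: one has a Cycle 1 DLT, and three others cannot restart within 28 days in later cycles. All of this is known at the look.

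- Section 8.7: 1 + 3 = 4 of 6, posterior 0.790, limit met.
- Section 7.2.2 to Day 28: 1 of 6, posterior Beta(2,10), P = 0.113, limit not met.

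**3. What can the Cycle 1 count reach?** Table 1 opens Phase II with at most 1 DLT in 6. If those six are the first six counted, the maximum is:

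| n | Maximum Cycle 1 count | Limit |
|---|---|---|
| 6 | 1 | 4 |
| 9 | 1 + 3 = 4 | 5 |
| 12 | 1 + 6 = 7 | 6 |
| 15 | 1 + 9 = 10 | 7 |

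The first two looks are then out of reach, late related deaths aside. For example, 1 Cycle 1 DLT + 1 late related death + 3 of 3 new subjects = 5/9. Two other readings change this:

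- Three subjects carried over at 0/3 (section 4.5): maximum 3 at n = 6, still below 4, but 6 at n = 9, above 5.
- Phase I subjects excluded (the synopsis read literally): both looks can be reached.

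**4. Chance of stopping by n = 15.** No rates are given in the documents, so these are assumptions. Each subject independently has a Cycle 1 event with probability 0.20; late events raise the any-time rate to 0.30, 0.40 or 0.50. Results are conditional on 0 or 1 Cycle 1 DLT in the first six, except where stated.

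Cycle 1 count, exact binomial recursion: 0.25%. Without the condition (Phase I subjects excluded): 4.0%.

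Any-time count, simulation of 2 million trials before conditioning:

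| Late events known at each look | Any-time 30% | 40% | 50% |
|---|---|---|---|
| For all subjects | 9% | 35% | 68% |
| For all but the latest 3 enrolled | 6% | 22% | 48% |
| For all but the latest 6 enrolled | 3% | 12% | 27% |

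**The case against.** The best reply is that nothing here commands opposite actions. Neither 7.2.2 nor the synopsis orders the study to continue below its limit. Section 8.7 is the section on stopping rules, and every event counted in 7.2.2 is also counted in 8.7. Read together, 8.7 compels termination whenever its limit is met, and the other two are narrower restatements. Much of this stands: a reader might infer that 7.2.2 instructs continuation, and it does not. But no text gives 8.7 precedence, and 7.2.2 is the statistical section that defines the interim safety analysis.

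Other stronger readings also go too far:

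- *Three different windows.* In substance there are two. Section 7.2.2 through 3.2, and the synopsis, are both Cycle 1 rules with a grade 5 exception. The wording on events beyond the DLT window leaves 7.2.2 slightly open, but that sentence concerns the RP2D.
- *Late toxicity is ignored outside 8.7.* It is not. In the six-subject example the three late cases would bear on the RP2D, which could be lowered. What is missing is a numeric limit.
- *The Cycle 1 rule is idle before n = 12.* This holds only if six Phase I subjects are the first six counted. An idle look at n = 6 is also harmless in itself, since the 3+3 rule is stricter.
- *The 0.25% shows a weak rule.* A Cycle 1 rate of 20% lies below the ceiling, so rare stopping there is proper behavior. The figure shows only how far the two counts diverge.

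Two practical objections stand. The looks have no stated data cut-off, so an any-time count depends on when it is taken. Section 7.7 also defines the Phase II tolerability population by the 28-day window, which could be mistaken for the stopping-rule denominator.

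**Conclusion.** The inconsistency is real and should be corrected. A mandatory termination limit can be met under 8.7 and not under 7.2.2 or the synopsis, with the same subjects: 4/6 (79%) against 1/6 (11%) in the example. That rests on the text alone, reading 7.2.2 as the Day 28 definition plus related grade 5 events. The synopsis differs in population as well.

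The stopping probabilities only illustrate, because they depend on the assumed rates, on independence between subjects, and on how soon late events are known. The finding that the Cycle 1 count cannot stop at n = 6 or n = 9 is conditional on six subjects carrying over and on no late related death.

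**What to change.** In 7.2.2 and in the synopsis stopping-rule text, replace the DLT event with *unacceptable toxicity (section 8.7 definition), counted over subjects at the RP2D beginning with the first six treated there*, and change the remaining mentions of DLT in those two texts to match. This also removes the population mismatch. Add that each look counts all events known at that date for every subject enrolled at the RP2D; this settles the denominator against 7.7. It makes the count reproducible but does not remove its dependence on timing.

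Leave the sentences on late events and the RP2D in 3.1.2, 3.2 and the synopsis unchanged. Limits, prior, Simon counts and sample size stay as they are.

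The cost is wording; adverse events and treatment holds are already recorded. The downside is more frequent stopping than under a Cycle 1 count: in the illustration, 3% to 9%, 12% to 35% and 27% to 68% at any-time rates of 30%, 40% and 50%. Rates near the ceiling are plausible. Section 1.4.2 reports grade 3 or higher non-hematologic toxicity in 6/19 (32%) on everolimus alone, and four grade 4 hematologic toxicities besides. That trial used 10 mg, against 5 mg here. Section 8.7 already applies this ceiling and prior to the any-time count, so the edit adds no new limit. If the sponsor thinks them unsuitable for up to 24 cycles, that is a separate decision to state openly.

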7.3 Subject Population for Analysis – Phase I

In order to be included in the tolerability review, a subject must have received the cohort-specific dose of itacitinib and everolimus for at least 75% of the days during the 28-day DLT surveillance period or have experienced a DLT. Additional subjects may be enrolled to achieve a minimum cohort size of 3-6 (see Figure 1) should withdrawal or dose interruptions/reductions result in a subject being non-evaluable. Subjects who receive at least one dose of the combined treatment (itacitinib and everolimus) will be assessed for adverse events, response, survival and exploratory analyses (FACT-lym, resolution of B symptoms or pruritus).

Page 54 of 72

7.4 Primary Analyses

The primary endpoint of Phase I is safety and tolerability by evaluating the frequency, duration, and severity of AEs as assessed by the investigators using CTCAE v5.0 criteria. The primary endpoint of Phase II is CR rate; a subject will be considered as a complete responder if his or her best overall response is CR on the Lugano Classification (Appendix 13.4) (Cheson et al 2014). The rate of responders will be estimated together with 90% confidence interval (CI). The study will be considered successful if the total number of complete responders is ≥ 2 in Phase II.

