Up to 2 years (24 cycles; each cycle is 28 days) of active therapy. Additional cycles of investigational treatment may be added if in the opinion of the investigator that the benefit risk ratio for the subject continues to be favorable. Subjects who discontinue study treatment will be followed for disease status, subsequent anticancer treatments, and survival for up to 2 years from completing end of treatment (EOT) visit. The study will end after the last subject completes 2 year follow-up or earlier once all subjects have discontinued study treatment, all subjects have died, have withdrawn consent, or are lost to follow-up.

Statistical Methodology

Sample size determination: Phase I portion of the study will utilize the standard 3 + 3 design with 6 to 15 patients enrolled. At least 6 patients will need to be treated at recommended phase 2 dose (RP2D) before proceeding to Phase II. A Simon optimal 2-stage design will be implemented to rule out the null CR rate of 5% against the alternative of 25% CR rate that might lead to larger, confirmatory studies. For 80% power and 5% alpha level, the first stage will enroll up to 9 evaluable subjects. If by week 16 there are no responders from the first 9 evaluable subjects with CR, the study will be stopped. Otherwise, additional subjects will be enrolled for a total of 8-17 evaluable treated at RP2D.

The study will be considered successful if 2 or more subjects achieve CR. Evaluable subject is defined as any subject who received at least 21 days of therapy and with at least one efficacy evaluation measured.

General data analysis plan: Descriptive statistics such as mean, standard deviation, median and range for continuous variable, and percentage for categorical variables will be computed. For the safety objective, all AEs will be listed and tabulated by organ system and in CTCAE preferred terms. Point estimate of the true AE rate and 90% exact confidence intervals will be computed. For the primary efficacy objective, a two-sided 90% confidence interval will be calculated for the CR rate as well as for the ORR. Duration of response, PFS, and OS will be summarized using Kaplan-Meier curve, and median survival time will be estimated with the associated 90% CI. FACT-Lym questionnaires will assess health related QOL.

Safety Evaluations

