7.2.1 Interim Efficacy Analysis

The efficacy analysis is based on Simon 2 stage optimal design and will be performed after the enrollment of the first 9 evaluable subjects. If there are no responders with CR from the first 9 evaluable subjects (at the 8 week or 16 week response assessment, at any itacitinib dose level), the null hypothesis (CR rate of 5% or lower with the new combination) will be considered as supported, and the study will be terminated. If there are no CRs in the first three (3) patients (week 8 or 16), we will suspend the study enrollment and await final response assessment on all 9 patients (6 in Phase I and 3 in Phase II). The study will be considered successful if the total number of subjects with CR is ≥ 2 in Phase II (at the 8 week or 16 week response assessment).

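### The primary CR rate has no estimator or interval suited to the two-stage design, and a stop at 0/9 is read as support for the null when it justifies only a futility stop

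*Combined protocol and SAP*

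**What the plan says.** The synopsis and Section 7.1 set up a Simon optimal design to "rule out the null CR rate of 5% against the alternative of 25% CR rate"; Section 7.1 states that "a total of 17 subjects at RP2D will be needed for 80% power at 1-sided alpha = 0.05 level". The stage 1 rule in the synopsis is: "If by week 16 there are no responders from the first 9 evaluable subjects with CR, the study will be stopped".

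For the primary estimate, Section 7.4 gives "The rate of responders will be estimated together with 90% confidence interval (CI"), and the synopsis gives "a two-sided 90% confidence interval will be calculated for the CR rate as well as for the ORR". No interval method, estimator or allowance for the stage 1 stop is named for the CR rate. The only place that names an interval type is the synopsis sentence on adverse events: "Point estimate of the true AE rate and 90% exact confidence intervals will be computed".

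On a stage 1 stop, Section 7.2.1 says "the null hypothesis (CR rate of 5% or lower with the new combination) will be considered as supported". Section 8.7 defines the null in the same way; Sections 3.1.3 and 7.1 also call it supported, without the words on 5% or lower. The success rule in Section 7.4 is: "The study will be considered successful if the total number of complete responders is ≥ 2 in Phase II".

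**The concern.** Trials that reach 17 subjects have already shown at least one CR in the first 9. The final count is therefore not an ordinary binomial count on 17, and a trial that stops early reports 0 with no chance to recover. A raw proportion is then biased, and an interval built for a single sample of 17 need not match the two-stage test. With no method named, the choice can be made after the data are seen, on the trial's primary endpoint.

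The wording on 0/9 is a separate matter. Failing to reject a null is not evidence for it. If the trial stops at stage 1, the plan's wording invites a report that the combination's CR rate is 5% or lower, which nine subjects cannot show.

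**Working it through.** **Inputs.** p0 = 5%, p1 = 25%, one-sided alpha 0.05, power 80%, N = 17 (synopsis, Section 7.1); stage 1 of 9, stop at 0 CRs (synopsis, 3.1.3, 7.2.1); success at 2 or more CRs (7.4). Assumption: exactly 9 then 17 evaluable subjects, all at the RP2D. Write q = 1 − p.

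**The design reproduces.** A search over two-stage designs that minimises the expected sample size under p0 gives stop at 0/9, then reject at 3 or more of 17.
- P(continue and at least 3 CRs) = 1 − q^9 − 9pq^16 − 108p²q^15.
- At 5%: 1 − 0.6302 − 0.1981 − 0.1251 = 0.0466. At 25%: 1 − 0.0751 − 0.0226 − 0.0902 = 0.812.
- With the stated cut-off of 2, the last term drops out: alpha = 1 − 0.6302 − 0.1981 = 0.172, and power = 0.902.

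**Bias of the raw proportion** (0 if stopped at stage 1). E = [9p + 8p(1 − q^9)]/17, so bias = −(8/17)·p·q^9.
- p = 5%: −0.4706 × 0.05 × 0.6302 = −1.5 points.
- p = 10%: −0.4706 × 0.10 × 0.3874 = −1.8 points.
- p = 25%: −0.4706 × 0.25 × 0.0751 = −0.9 points.

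**UMVUE** for s CRs in 17: Σ C(8,x−1)C(8,s−x) / Σ C(9,x)C(8,s−x), over x ≥ 1. This gives 1/9, 16/108 and 120/624 for s = 1, 2, 3.

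**90% intervals.** The stagewise limits order the stage 1 stop lowest, then total CRs. The lower limit solves P(continue and total ≥ s) = 0.05. The upper limit solves P(stop) + P(continue and total ≤ s) = 0.05.

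| CRs | Raw | UMVUE | Clopper-Pearson | Two-stage |
|---|---|---|---|---|
| 1/17 | 5.9% | 11.1% | 0.3–25.0% | 0.6–29.9% |
| 2/17 | 11.8% | 14.8% | 2.1–32.6% | 2.4–34.3% |
| 3/17 | 17.6% | 19.2% | 4.99–39.6% | 5.14–40.1% |

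Other fixed-sample lower limits at 3/17 are Wilson 7.3%, Agresti-Coull 6.7%, Jeffreys 6.7% and Wald 2.4%.

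**Coverage of Clopper-Pearson on the two-stage path**, p from 0.5% to 60%. Two-sided coverage is never below 90.8%, and lower-tail error never exceeds 5.0%. Upper-tail error peaks at about 6.4%, just above p = 32.6%, where 0/9, 1/17 and 2/17 all have upper limits below p. At p = 32.65% it is q^9 + 9pq^16 + 108p²q^15 = 2.85% + 0.53% + 3.06% = 6.44%.

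**0/9.** The exact upper limit is 1 − 0.05^(1/9) = 28.3%, whether computed as a fixed sample or stagewise. Other methods give Agresti-Coull 26.9%, Wilson 23.1% and Jeffreys 18.7%. P(0/9) = q^9: 63.0% at p = 5%, 38.7% at 10%, 13.4% at 20%, 7.5% at 25%.

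**The case against.** A reader might infer that the plan prescribes a fixed-sample interval that contradicts the Simon test at 3/17. The documents do not support that. They name no method for the CR rate. The disagreement is 0.01 point under Clopper-Pearson, would print as 5.0%, and is absent under Wilson, Agresti-Coull and Jeffreys. Nor is 3 the plan's own cut-off: success is declared at 2. At 2/17 all five fixed-sample intervals and the two-stage interval contain 5%, so a better interval does not reconcile test and estimate there. The cause is the cut-off.

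Little validity is lost either. Clopper-Pearson keeps its two-sided 90% coverage on this design, and the bias is downward, hence conservative for a claim of activity, and small beside intervals 25 to 35 points wide. That stands, and it limits the point to an improvement. What remains is the missing specification, the avoidable bias and the upper-tail error.

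A reader might also tie the 0/9 wording to neglect of the two-stage design. It is not: the exact limit is 28.3% either way. One can defend the word as a choice between two stated rates, since 0/9 is 0.630/0.075 = 8.4 times likelier at 5% than at 25%. But Sections 7.2.1 and 8.7 define the null as 5% or lower, and 0/9 is also unremarkable at 10%. That the result would be published as proof of a low rate is conjecture, since Section 7.4 already requires an interval.

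**Conclusion.** The point holds as a cheap improvement to the primary estimate plus a correction of wording. The plan leaves the estimator and interval for its primary endpoint open, in a design where the raw proportion is low by about 1 to 2 points and a Clopper-Pearson upper limit is low by up to about 5 points (at 1/17). It does not show that an ordinary exact interval would be invalid overall.

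The 0/9 conclusion is unsupported under each method that gives a usable interval: upper limits run from 18.7% to 28.3%, all far above 5%. The result justifies stopping for futility and no more.

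The figures rest on 9 then 17 evaluable subjects at the RP2D. The documents also give at least 14 evaluable (3.1.3, 7.1) and 17 to 20 treated at the RP2D (4.5). They count the first 9 at the RP2D (3.1.3) or at any itacitinib dose level (7.1, 7.2.1); Section 8.7 says both. The larger defect is the cut-off: 2 or more of 17 carries an alpha of 17.2% against the stated 5%, which needs 3 or more.

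**What to change.** First reconcile the success cut-off with the stated alpha, and fix the stage 1 and final denominators; a two-stage estimator needs a defined sampling path.

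Then, in Section 7.4 and the synopsis, state: *The CR rate in the Simon cohort will be reported with the UMVUE and a two-sided 90% CI based on the stagewise ordering of the two-stage design, adapted to the actual final N; the raw proportion will be given as a supplement.*

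In Sections 3.1.3, 7.1, 7.2.1 and 8.7, replace the statement that the null is supported with: *The study stops for futility; H0 is not rejected; the result is reported with its 90% CI (0 to 28.3% for 0/9).*

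The cost is SAP wording and standard software, with no added subjects or visits. The downside is a slightly wider interval at low counts, mainly through a higher upper limit.

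### Success is declared at 2 or more CRs, but the stated Simon optimal design (5% vs 25%, 9 then 17 subjects) needs 3 or more; the type I error is about 17%, not 5%

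*Combined protocol and SAP*

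**What the plan says.** The Study Summary says the design is to "rule out the null CR rate of 5% against the alternative of 25% CR rate". Section 7.1 names the method ("Using a Simon 2-stage optimal design") and says that "a total of 17 subjects at RP2D will be needed for 80% power at 1-sided alpha = 0.05 level". The futility rule in the same section ends the trial in this case: "If by the 16 week visit there are no responders with CR from the first 9 evaluable subjects".

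The success rule is given in five places, always with a threshold of 2:

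- Study Summary, Statistical Methodology: "The study will be considered successful if 2 or more subjects achieve CR".
- Section 3.1.3: at least 2 subjects with CR in Phase II.
- Section 7.2.1: "The study will be considered successful if the total number of subjects with CR is ≥ 2 in Phase II", judged at week 8 or 16.
- Section 7.4, the primary analysis: "The study will be considered successful if the total number of complete responders is ≥ 2 in Phase II".
- Section 8.7: the same rule as Section 7.2.1.

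No section gives a threshold of 3, and none states a type I error other than 5%. Section 3.1.3 counts six Phase I subjects as accrued to Phase II.

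**The concern.** A Simon design is usually tabulated with a bound r, the largest number of responses that does not reject the null. For these inputs r is 2 out of 17, so success starts at 3. The plan has the sample sizes of that design but sets success one response lower.

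This rule decides the primary conclusion. Section 7.1 treats a 5% CR rate as no clinical benefit over everolimus alone, and 25% as a rate that might justify larger confirmatory trials. If the threshold is one too low, an inactive addition to everolimus is carried forward much more often than the stated 5% allows, and readers of the result would not know it.

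**Working it through.** **Inputs.** p0 = 0.05 and p1 = 0.25 (Study Summary; Section 7.1). One-sided alpha 0.05, power 80%, N = 17 at the RP2D, n1 = 9, stop at 0 CRs of 9 (Section 7.1). Success at R = 2 or more CRs (five places above). The calculation takes the first 9 to be part of the 17.

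**Formula.** With b(n, x, p) the binomial probability and T(n, k, p) = P(X ≥ k):

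P(success) = Σ over x = 1 to 9 of b(9, x, p) × T(8, R − x, p)

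This is the type I error at p = 0.05 and the power at p = 0.25.

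**Step 1: reproduce the plan's sizes.** I searched all two-stage designs with total N below 30 for alpha ≤ 0.05 and power ≥ 0.80, minimising expected N under p0. The result is n1 = 9, stop at 0, N = 17, success at **3 or more**, with alpha 0.0466, power 0.8122 and expected N of 11.96 under p0. The sizes match the plan exactly. The minimax design is 12 then 16, also with success at 3 or more, so it is not the plan's design.

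**Step 2: the rule as written (R = 2).**

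- p = 0.05: one CR in stage 1 and at least one in the next 8, 0.2985 × 0.3366 = 0.1005; two or more CRs in stage 1, 0.0712. Sum **0.172**.
- p = 0.25: 0.2253 × 0.8999 = 0.2027, plus 0.6997. Sum **0.902**.

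**Step 3: the design's own threshold (R = 3).**

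- p = 0.05: 0.2985 × 0.0572 = 0.0171; 0.0629 × 0.3366 = 0.0212; three or more in stage 1, 0.0084. Sum **0.047**.
- p = 0.25: 0.2253 × 0.6329 = 0.1426; 0.3003 × 0.8999 = 0.2703; 0.3993. Sum **0.812**.

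**Step 4: other totals.** The documents do not give a single N at the RP2D. Sections 3.1.3 and 7.1 say at least 14, the Study Summary 8–17, and Section 4.5 expects 17–20. With the stop at 0 of 9:

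| N | ≥2: alpha / power | ≥3: alpha / power |
|---|---|---|
| 14 | 0.139 / 0.872 | 0.029 / 0.711 |
| 17 | 0.172 / 0.902 | 0.047 / 0.812 |
| 18 | 0.182 / 0.908 | 0.053 / 0.835 |
| 20 | 0.200 / 0.915 | 0.066 / 0.868 |

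**Step 5: CRs counted only among new Phase II enrollees.** Here the first 9 are 6 Phase I and 3 new subjects, as in Section 7.2.1, and success is 2 or more CRs among the new subjects:

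| New subjects | Alpha | Power |
|---|---|---|
| 8 | 0.043 | 0.61 |
| 11 | 0.066 | 0.76 |
| 14 | 0.089 | 0.84 |
| 17 | 0.111 | 0.88 |

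None of these has both alpha ≤ 0.05 and power ≥ 0.80.

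**The case against.** The strongest reply is that 17% belongs to one reading at one sample size. The rule says 2 or more CRs in Phase II. If that means new enrollees only, alpha runs from 0.043 to 0.111 (step 5), and with 8 new subjects it is below 5%. But power there is only 0.61, and Section 3.1.3 counts the six Phase I subjects in Phase II, so this reading neither fits the text well nor rescues the design.

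A second reply is that a threshold of 3 is not safe at every N the documents allow. This stands. At 14 subjects power falls to 0.711, and from 18 upward alpha exceeds 5%. The correction works only if the denominator is fixed as well.

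A third is that Sections 7.1, 7.2.1 and 8.7 let the first 9 come from any itacitinib dose level, while Section 3.1.3 (and Section 8.7 itself) says the RP2D. If subjects at another dose enter stage 1, neither 0.172 nor 0.047 is exact. This also stands as a condition on the figures, but it does not make 2 the right threshold for a 9/17 design.

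The 90% confidence interval in Section 7.4 does not settle the matter. It is there for estimation, and the exact lower limit even for 3 of 17 is 4.99%. The argument rests on the two-stage error rates.

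**Conclusion.** The concern holds. The stated sizes, alpha and power fit together only with success at 3 or more CRs of 17. As written, the primary rule has a type I error of 0.172, about 3.4 times the stated 0.05 (0.172 / 0.05), and power of 0.902.

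These figures assume 17 evaluable subjects at the RP2D, Phase I subjects at that dose included, with the first 9 among them and binding termination at 0 of 9. At the other totals in step 4, 14 to 20, the threshold of 2 still gives 0.139 to 0.200. This must be fixed because it governs the trial's main conclusion. The documents do not show how the threshold of 2 was chosen, and the conclusion does not depend on the reason.

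**What to change.** In the Study Summary and Sections 3.1.3, 7.2.1, 7.4 and 8.7, define success as 3 or more CRs among the 17 evaluable subjects treated at the RP2D, with Phase I subjects at that dose included.

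For the threshold to deliver 5% and 80%, make 17 the analysis denominator throughout. That means reconciling the figures of at least 14, 8–17 and 17–20, and stating that the first 9 belong to the 17. If the number evaluable may differ from 17, give the threshold and its error rates for each possible total in advance.

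If the sponsor prefers to keep 2 or more, Section 7.1 should state the actual type I error of about 17% and power of about 90% at N = 17 and drop the 5% claim.

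The cost is a wording amendment. No subjects are needed beyond the planned 17, and power at 17 is 81%, above the stated 80%. The price of the stricter threshold is the drop in power from 90% to 81%.
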